9.1.5. Suspected unexpected serious adverse reaction (SUSAR)

A SUSAR is a SAE that is unexpected and thought to be possibly, probably or definitely related to an IMP.

9.1.6. Relevant medical event/ Emerging safety issue “fait nouveau”

Any new safety information which could significantly modify the evaluation of the benefit/risk ratio of the investigational medicinal product or the clinical trial, likely to affect the safety of participants or that could modify the investigational medicinal product administration, the trial documentation or the conduct of the trial (eg: a significant hazard to the subject population such as unexpected occurrence of an unwanted reaction, serious adverse event related to study procedure, lack of efficacy of an investigational medicinal product used for the treatment of a life-threatening disease).

For all safety issues qualifying the definition of New Event or Urgent Safety Measure and therefore, requiring immediate notification, sponsor will contact the CA, IRB, EC and ARS (France) without delay in order to share any relevant information for the evaluation of the event and communicate any urgent safety measures implemented if necessary.

Expedited reporting to CAs, ECs and investigators of each site will be managed by SGS Medical Affairs according to the SOP “Processing and Reporting of Individual Serious Adverse Events of Interventional Clinical Trials”, the ICH guideline E2A “Note for Clinical Safety Data Management” and the Safety Management Plan. CRAs will be in charge to inform investigator of each site of any relevant medical event/emerging safety issue occurring during the study. An Acknowledgment of Receipt will be completed and signed by the investigator and then retrieved by the CRA.

9.1.7. Definitions of Adverse Event Severity

AEs must be graded by a medically qualified person as being mild, moderate, severe or life-threatening and their approximate duration given. Definitions of severity are as follows:

- Mild: An AE that requires minimal or no treatment and does not interfere with daily activities
- Moderate: An AE that is sufficiently discomforting to interfere with normal activities
- Severe: An AE that is incapacitating or prevents normal activities and may require systemic drug therapy or other treatment
- Potentially Life-Threatening: An AE that requires immediate intervention to prevent death

"Life-threatening" refers to an AE in which the participant was at risk of death at the time of the event, it does not refer to an AE which hypothetically might have caused death if it were more severe.

The investigator will assess the severity of an AE according to the "Guidance for Industry: “Toxicity Grading Scale for Healthy Adult and Adolescent Volunteers Enrolled in Preventive Vaccine Clinical Trials” (Appendix 2).

9.1.8. Definitions of Adverse Event Causality

The Investigator will document in his/her opinion the relationship of the AE to the study drug according to the following definitions:

- **Definitely:** Temporal relationship to the administration of the study drug and course following a known reaction pattern
- **Probably:** Good reasons and sufficient documentation to assume a causal relationship
- **Possibly:** A causal relationship is conceivable and cannot be dismissed
- **Unlikely:** The event is most likely related to an etiology other than the trial treatment
- **Not Related:** No temporal relationship to the administration of the drug or other factors have caused the event.

9.1.9. Expectedness

Expectedness will be determined considering the current IB.

- **Expected:** A SAR that is listed in the current IB
- **Unexpected:** An AE that is not listed in the current IB or that differs due to greater severity or greater specificity
- All SAEs assessed as unexpected and suspected to be (at least possibly) related to the IMP qualify for a SUSAR and require expedited reporting.

9.1.10. Outcome

- **Recovered/Resolved:** A participant has recovered from an AE, when all signs or symptoms returned to normal
- **Recovered / Resolved with sequelae:** An AE is stabilized when, according to the investigator, the participant is in a clinically stable condition. This term should only be used for chronic conditions and for a given participant only when he/she has completed the study
- **Recovered with sequelae:** As a result of the SAE, the subject is suffering from persistent or significant disability/incapacity (e.g. became blind, deaf, paralyzed). Any AE recovered with sequelae should be rated as an SAE since an SAE criterion is fulfilled
- **Not Recovered/Not Resolved:** An AE currently ongoing
- **Recovering / Resolving:** An AE ongoing at the participant's last visit
- **Fatal:** An AE that caused death
- **Unknown:** AE outcome is unknown by the investigator at the participant's last visit

9.1.11. Fever and respiratory tract disease

In case of fever (body temperature $\geq 38^{\circ}\text{C}$), respiratory tract disease (persistent dry (non-productive) cough, tachypnea or dyspnea) or unexplained, severe symptoms triggering the nasal swab are reported as AE a root cause clarification has to be induced to explore if the AE may be due to a wild type COVID-19 infection.

Participants should be trained during each visit to contact the site via phone in case of above-mentioned AEs to scheduled proper on-site visits to performed further actions.

Therefore, the investigator should make every effort to diagnose the etiology, considering typical symptoms as outlined in the COVID-19 Clinical Working Group, dated 21-Apr-2020 “ Criteria for clinical diagnosis of incident COVID-19 disease in adults in interventional trials” .

In case of contact with a confirmed case or in case of suspected SARS-CoV-2 infection given by the presence of any symptoms listed below, the participant will be invited, according to the local procedure to attend an unscheduled visit or to contact his/her GP (see section 7.2.14). During this visit, vital signs including SpO₂, Respiratory Rate, Heart Rate, Body Temperature will be measured and a collection of upper respiratory tract specimens (nasal swab) for testing by reverse transcription polymerase chain reaction (RT-PCR) will be performed for the diagnosis of a recent infection.

Symptoms triggering the nasal swab are:

- Fever,
- cough with or without production (sputum or blood),
- Sore throat,
- Rhinorrhea,
- Dizziness,
- Wheezing,
- Chest pain,
- Myalgia,
- Arthralgia,
- Fatigue,
- Dyspnea,
- Headache,
- Altered consciousness / confusion,
- Abdominal pain,
- Vomiting / Nausea,
- Diarrhea,
- Conjunctivitis,
- Skin rash,
- Ageusia,
- Anosmia

Data related to date of symptoms onset, source of possible exposure (e.g. contact with a confirmed case within 14 days prior to symptoms onset), physical examination, vital signs measurement, results of laboratory tests will be documented in the participant' source data. The result of the SARS-CoV-2 PCR will be documented in the participant' source data and in the eCRF. In case of confirmed SARS-CoV-2 infection and according to the severity of the disease, the participant will be referred to a specialist and will be followed according to the national guidelines.

Virologically-confirmed COVID-19 clinical disease is defined as:

- An acute respiratory illness that is clinically consistent with COVID-19 based on presence of at least two of the following:
- Fever or history of new-onset fever (defined as body temperature of >38.0°C irrespective of method)

- New onset *lower* respiratory tract disease (LRTI) (any):
 - Persistent dry (non-productive) cough
 - Tachypnea or dyspnea
 - Low peripheral oxygen saturation (< 95%)
 - Radiographic findings consistent with LRTI
- New onset systemic symptoms consistent with viral illness (any):
 - Sore throat
 - Myalgia
 - Chills
 - Loss of smell or taste
 - Headache
 - fatigue
 - Congestion or runny nose
 - Nausea or vomiting
 - Diarrhea

AND

- Positive SARS-CoV-2 specific reverse transcriptase polymerase chain reaction (RT-PCR)

Severe COVID-19 clinical disease is defined as

- Virologically-confirmed COVID-19 clinical disease

AND

- A NEWS-2 score of >6

COVID-19-naive: Person testing negative for anti-SARS-CoV-2 antibodies at baseline [using an antibody test with high sensitivity]

Furthermore, the place of subject's residence, travel history and exposures to areas with known virus transmission within 15 days prior to the onset of symptoms have to be regarded when investigating a possible infection.

In case, the investigator cannot rule out a COVID-19 wild type infection, SARS CoV 2 PCR and serology will be performed.

If a subject is suspected/diagnosed with an actual COVID-19 infection he/she should not receive any subsequent study vaccination but should perform all visits for safety follow up reasons.

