3.3. Blinded / randomized cohorts

After DSMB review and positive recommendation, sponsor will decide to continue the study by the enrollment of the remaining 84 participants (“Main Cohorts”), in a blinded randomized manner, in the low dose group (cohort A) or in high dose groups (cohort B and C).

Table 1: Treatment groups allocation

| Cohort | Treatment | Injection 1 D0 | Injection 2 D28 | Number of participants | | |
|--------|----------------------|-------------------|--------------------|------------------------------|------------------------------|---------|
| | | | | COVID-19 vaccine Sentinel | COVID-19 vaccine Main grp | Placebo |
| A | COVID-19 low Dosage | Vaccine | Vaccine | 3 | 21 | 6 |
| B | COVID-19 high Dosage | Vaccine | Vaccine | 3 | 21 | 6 |
| C | COVID-19 high Dosage | Vaccine | Placebo | 0 | 24 | 6 |

Participants will be observed closely for safety and immunogenicity from the first injection to the end of study.

The investigator, and site personnel performing study related assessments, all participants, as well as the sponsor’s representatives involved in the monitoring and conduct of the study will be blinded.

Only site personnel performing randomization, preparation of IMP and monitoring of the IMP handling process will be unblinded as well as the DSMB members (excluding observing DSMB members who will only have access to blinded safety report).

During the follow up phase (after all subjects have completed V6), the head of vaccine programs of Institut Pasteur and a project manager from the vaccine developer (Themis Bioscience GmbH a subsidiary of Merck & Co., Inc., Kenilworth, New Jersey USA,) will have access to the unblinded data for the purpose of immunogenicity assessment. In the current pandemic, rapid assessment of the potential of the vaccine, including the balance of safety and immunogenicity is required to move promising candidates forward as quickly as possible. All data will be stored on a secured server accessible with a login and password to which only the unblinded person has access. The risk of impact on the study is minimized as unblinding will occur when the treatment phase will have been completed, the analyses have been defined, and the unblinded personnel is not involved in the clinical evaluation and management of the participants.

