4.8. Individual participants halting rules

The following are specific criteria for discontinuing individual participants from further vaccination, but not from completing scheduled follow-up assessments, unless the participant is explicitly withdrawn from the study:

- Participants who experienced a Serious Adverse Reaction (i.e. a Serious Adverse Event considered at least possibly related to vaccine).
- Participants who experienced a severe (grade 3 or higher) non-serious adverse event considered as at least possibly related to the vaccine
- Participants who develop a medical condition for which continued participation, in the opinion of the investigator, would pose a risk to the participant or would be likely to confound interpretation of the results
- Participants with a confirmed SARS CoV-2 infection given by a positive RT-PCR or a positive serology.
- Participants who donate whole blood or blood derivatives, tissue or organ all along the study.
- Participants who become pregnant during the treatment phase of the study.
- Participants not using a reliable method of contraception
- Participants who experience hypersensitivity reaction such as anaphylaxis within 24 hours or generalized urticaria within 72 hours after administration of the study vaccine
- Participants who use immunosuppressive drugs
- Participants who receive immunoglobulin or other blood product before study completion.
- Participants who live and/or work with severely immunocompromised people, pregnant women, lactating women, children under 12 months old, or any other individual that, in the judgment of the investigator, might be at increased risk from the first vaccination (D0) up to 28 days after the second vaccination (D56).

If any of these occur, appropriate measures to treat the participant will be taken and the participant will be asked to perform an ET visit if the participant is withdrawn (for any reason) from the study. The sponsor will be notified immediately.

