4.9. Study halting rules, early study termination, end of study

4.9.1. Study halting rules

The study could be temporally suspended, pending a full DSMB safety review. The criteria for considering a contraindication or preventive action to the start of the treatment of cohort B and C (increasing dosage) or administration of the COVID-19 vaccine to subsequent subjects in the current cohort will be:

- A serious adverse reaction (i.e. a serious adverse event considered at least possibly related to the study vaccine) in one subject.
- The occurrence of clinically significant severe (grade 3 or higher) non-serious adverse events considered as at least possibly related to the vaccine administration in two subjects in the same cohort, independent of within or not within the same system-organ-class. Both clinical and laboratory abnormalities are considered.

- Any onset of AESI assessed as related to the vaccine by the investigator or by the sponsor.

After complete safety review by the DSMB and taking into account its recommendation, sponsor will decide if the study (i.e. new inclusion and/or new injection) should be discontinued, continued after protocol modifications or resumed according to the protocol.

In case of study discontinuation, the Competent Authorities (CA) and Ethics Committees (EC) will be informed and all participants still in follow-up will be contacted for attending an Early Termination visit (see section 7.2.13).

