8.2. Participant Diary

The participant will receive a diary on each vaccination day (visit 1 and 4) for 14 \pm 1 days completion. They will be requested to record any local or systemic reaction (vaccination day included) and body temperature. In this frame, participants will receive a ruler to measure the size of local reaction if occurs and a thermometer to measure oral body temperature.

Solicited local and solicited systemic reactions will be assessed by the participants themselves by checking for presence of the listed symptoms and measuring the size of the affected area where appropriate (a template will be provided for local reaction grading, as shown in Appendix 3). The diary will also provide space for recording unsolicited AEs and concomitant medication.

Recording should be done approximately at the same time each day, starting on the day of vaccination.

The participants' diaries will be collected and verified for completeness by the investigator. Any symptoms recorded in the participant diaries will be documented in the source data by the investigator or authorized delegates. The investigator will re-evaluate the severity of the reported local and systemic reactions according to the "Toxicity Grading Scale for Healthy Adult and Adolescent Volunteers Enrolled in Preventive Vaccine Clinical Trials" (Appendix 2). After assessment of the Investigator, clinically significant symptoms (i.e. moderate/severe) and mild symptoms for which a treatment is required will be reported as Adverse Events in the eCRF.

The diary includes the following:

- **Solicited systemic AEs:** Myalgia (osteomuscular pain), rash, nausea, vomiting, fever (body temperature $\geq 38^\circ$), headache and fatigue.
- **Solicited local reaction to injection:** Pain, itching, erythema (redness), swelling, induration.

these should also be documented in the participant' source data and in the eCRF.

In addition, body temperature will be checked during 14 \pm 1 days following each injection and fever will be graded by the investigator according to "Toxicity Grading Scale for Healthy Adult and Adolescent Volunteers Enrolled in Preventive Vaccine Clinical Trials" (Appendix 2).

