Serum antibody responses (IgG and IgM) to the SARS-CoV-2 nucleoprotein (N) will be measured using the Roche-Elecsys® Anti-SARS-CoV-2 immunoassay. The assay is a double-antigen sandwich assay using electro-chemiluminescence for detection (electro-chemiluminescence immunoassay, ECLIA). The analyses will be performed at PPD Central Labs.

As the N protein is not included in the COVID-19 vaccine candidate, assessment of antibody responses to the N protein differentiates immune responses to vaccination from immune responses to SARS-CoV-2. Positive anti-N results will indicate that the subjects have been exposed to the SARS-CoV-2 virus. As not all subjects might experience COVID-19 disease, this analysis will detect asymptomatic cases.

ELISA for measles serum antibodies:

IgG to measles will be assessed using the commercially available ELISA kit. The ELISA analyses will be performed at BioAster, Lyon, France.

Assessment of the baseline of anti-measles antibodies of the subjects at baseline (day 0) is important to assess any potential impact of pre-existing immunity on the take of the vaccine. In addition, IgG levels to measles are assessed after the first and second immunization. This provides a control to assess if the vaccine backbone elicited an immune response in a given subject in case no response to the S protein was detected.

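### Section 9.1.11 bars injection 2 on suspected infection, which any solicited systemic reaction satisfies; sections 4.8, 7.2.6 and 7.2.13 would let the same participant be dosed

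*Protocol*

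**What the plan says.** The condition for withholding injection 2 appears in several places in the protocol.

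- **Section 9.1.11** invites a participant to an unscheduled visit or to the GP "in case of suspected SARS-CoV-2 infection given by the presence of any symptoms listed below". The list has 20 entries, with no limit on severity or on time since injection. Later the section states: "If a subject is suspected/diagnosed with an actual COVID-19 infection he/she should not receive any subsequent study vaccination".
- **Section 4.8** stops further vaccination for "Participants with a confirmed SARS CoV-2 infection given by a positive RT-PCR or a positive serology". A non-serious adverse event stops it only at grade 3 or higher and if at least possibly related to the vaccine. A further bullet covers conditions that the investigator considers a risk to the participant or likely to confound the results.
- **Section 7.2.13**, Belgian site, withdraws a participant from dosing after a positive test. The French procedure lists examinations and gives no dosing rule.
- **Section 7.2.6** (Visit 4) lets the investigator give injection 2 later in case of acute disease or fever, with withdrawal only if an individual halting rule is met.
- **Section 8.2** lists the solicited systemic reactions as "Myalgia (osteomuscular pain), rash, nausea, vomiting, fever", followed by headache and fatigue.
- **Section 12.4** explains which antigen tells infection from vaccination: "As the N protein is not included in the COVID-19 vaccine candidate, assessment of antibody responses to the N protein differentiates immune responses to vaccination". The contrast drawn there is with responses to the virus.

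**The concern.** Section 1.5 expects headache, myalgia, flu-like symptoms and fatigue after vaccination. Section 9.1.11 makes the same symptoms evidence of suspected infection and attaches a dosing bar to suspicion. Section 4.8 attaches its infection stop to confirmation. Two investigators following the protocol faithfully could decide differently on the same participant, and so could the two sites.

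This reaches the analysis. Section 2.2.1 makes the rate of solicited events after each injection part of the primary outcome. Section 12.1 requires two injections for the Per Protocol set, and section 12.4 names that set for the geometric mean titre (GMT) comparison. If injection 2 is withheld because of reactions to injection 1, both depend on who reacted.

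A smaller point belongs to the same repair. Section 4.8 accepts a positive serology as confirmation, and 9.1.11 orders serology when infection cannot be ruled out. Neither names the antigen, although the vaccine is meant to induce anti-spike antibody.

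**Working it through.** The protocol gives no figure to reproduce here: section 12.6 reports no formal sample size calculation, and no symptom rates are stated. The check is therefore mainly a comparison of texts.

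**1. Overlap of the two lists.** Solicited systemic terms (8.2): myalgia, rash, nausea, vomiting, fever, headache, fatigue, which is 7. On the 9.1.11 list: myalgia yes, skin rash yes, vomiting/nausea yes (one entry, two terms), fever yes, headache yes, fatigue yes. The overlap is 7 of 7 terms, taking up 6 of the 20 entries.

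**2. One participant under each passage.** Take a grade 1 headache two days after injection 1, with a negative PCR.

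| Passage | Condition | Result |
|---|---|---|
| 9.1.11, dosing sentence | suspected or diagnosed | barred; no sentence lets the negative PCR lift the bar |
| 4.8, infection bullet | positive RT-PCR or serology | not stopped |
| 4.8, reaction bullet | grade 3 or higher and at least possibly related | not stopped |
| 4.8, judgment bullet | investigator sees a risk or confounding | depends on the investigator |
| 7.2.13, Belgian site | positive test | not stopped |
| 7.2.13, French site | no dosing rule | no answer |
| 7.2.6 | health unchanged; fever or acute disease may delay | may be dosed, or dosed later |

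**3. Effect on the analyses if 9.1.11 is taken literally.** Let p_V and p_P be the proportions of vaccine and placebo recipients with at least one listed symptom before Visit 4. Group sizes from Table 1 are 24 per vaccine group (3 + 21, 3 + 21, 0 + 24) and 3 × 6 = 18 pooled placebo.

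- Expected number barred: 24 × p_V per vaccine group and 18 × p_P in pooled placebo. One barred participant is 1/24 = 4.2% of a vaccine group or 1/18 = 5.6% of pooled placebo.
- Loss is differential by arm only when p_V exceeds p_P, because placebo recipients with a listed symptom are barred too.
- The Per Protocol GMT shifts only if reactogenicity is associated with log10 titre. With no association the mean is unchanged and the standard error grows by a factor of 1/√(1 − p_V).
- In cohort C injection 2 is placebo, so the bar changes Per Protocol membership but not vaccine exposure.

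Neither p_V, p_P nor that association is in the protocol, so no size follows. By contrast, if a positive test is required, a grade 1 or 2 reaction with negative tests bars 0 participants by this route.

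**4. Serology.** The N-specific assay in 12.4 serves an exploratory endpoint and is not tied to the stop in 4.8. The schedule in 7.1 and Table 3 places diagnostic serology at screening and, afterwards, only as needed. A vaccine-induced false confirmation after injection 1 therefore needs two things: an ad hoc serology, and a kit that detects anti-spike antibody. The protocol does not state the kit's antigen.

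**The case against.** The best defence is that the two sentences in 9.1.11 do different jobs. The 20 symptoms are introduced as triggers for a nasal swab, and the dosing sentence comes after the diagnostic work-up and speaks of an actual infection. The section's opening is also narrower: besides fever and respiratory disease it asks for action when "unexplained, severe symptoms triggering the nasal swab are reported as AE a root cause clarification has to be induced". Sections 7.2.6 and 7.2.13 fit a reading in which testing settles suspicion, and the judgment bullet in 4.8 could cover some suspected cases, which narrows the gap.

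This may well be what was intended, and it is why the harm is conditional. It does not remove the contradiction. Suspected stands beside diagnosed as a separate trigger, the section itself says what suspicion consists of, and no sentence restores dosing after a negative result.

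Three stronger readings are tempting, and the documents do not support them:

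- *Most reactive vaccinees would be lost and the two-injection set emptied.* This needs symptom rates that the protocol does not give, plus literal application. Section 12.1 also keeps barred participants in the modified ITT set for safety and immunogenicity.
- *Vaccinees who mount a response would be stopped.* No diagnostic serology is scheduled between screening and Visit 4, and the kit is unnamed, so this is a clarification only.
- *The study halting rule in 4.9.1 has the same kind of fault, because it counts events "in two subjects in the same cohort, independent of within or not within the same system-organ-class" while the main cohorts are blinded and B and C share the Day 0 dose.* Sections 3.3 and 4.12 give an unblinded DSMB the task of determining whether halting rules are met. The text plainly counts by cohort, and pooling B and C would be a preference.

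**Conclusion.** The contradiction is established from the text alone: the same participant, with a mild solicited reaction and a negative PCR, is barred under 9.1.11 and may receive injection 2 under 4.8, 7.2.6 and the Belgian procedure. The overlap between solicited systemic reactions and suspected-infection symptoms is complete, 7 of 7.

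The statistical consequence is conditional on two assumptions: that 9.1.11 is applied literally, and that the vaccine causes more listed symptoms than placebo. Reaction rates after injection 2 and the Per Protocol GMT comparison would then rest disproportionately on vaccinees who tolerated injection 1. The modified ITT set limits this but cannot remove it, since a person not given injection 2 has no reaction to it to observe. No size can be put on the bias from this document.

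This should be fixed, because it governs who is re-dosed in a first-in-human trial and bears on a primary outcome. It does not show that the trial's results would be invalid.

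**What to change.** Reconcile sections 9.1.11, 4.8, 7.2.6 and 7.2.13 so that one stated condition governs injection 2 at both sites. The text should say whether that condition is suspicion or confirmation, what a negative work-up means for dosing, and how postponement at Visit 4 relates to it. The reference in 9.1.11 to section 7.2.14 should be corrected in the same pass, since the unscheduled-visit procedure is 7.2.13.

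At the same time, reconcile positive serology in 4.8 and the serology in 9.1.11 with section 12.4, so that an anti-spike response to the vaccine cannot be read as confirmed infection.

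Which clinical rule to adopt is for the sponsor and the DSMB. The cost is protocol wording and an instruction to the two sites, possibly with a change of local serology kit. Sample size, visits and planned analyses are unaffected.

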In case of presence of a clinically significant acute disease at the time of vaccination or presence of fever defined by a body temperature $\geq 38.0^{\circ}\text{C}$ 24 hours prior to the visit or at the time of vaccination, the participant may be vaccinated at a later date, at the discretion of the Investigator or withdrawn from the study if he/she has met an individual halting rules (see section 4.8). The subject must be followed until resolution of the event.

After injection, the participants will remain in the Investigational clinical site for medical supervision and monitoring for a minimum of 1 hour after injection.

The following assessment / activities will be performed 1 hour (± 15 min) after the second injection:

- Vital signs in sitting or supine position*.
- Local reaction of the injection site.

Participant will be provided with a new diary for the 14±1 following days. At the end of the visit, which lasts approximately 2 hours and once the study physician has determined that he/she is fit to be released, the participant will be discharged from the Investigational clinical site. The appointment for the phone call 2 will be scheduled and confirmed with the participants of the “Sentinel Groups and the appointment for the Visit 5 (Day 42) will be scheduled and confirmed with the participants of the “Main Cohorts.

7.2.7. Phone call 2 - “Sentinel Groups” (Day 29 - 24 hours ±3 hours after 2nd injection)

Twenty-four hours (±3 hours) after the second injection, participants of the “Sentinel Groups” will be contacted by phone for the monitoring of AE; AESI and SAE. Any changes in the concomitant medications, medical status and occurrence of AEs, AESI and SAE since the previous visit will be checked and recorded in the participant's source data and in the eCRF. In case of AE corresponding to the definition of SAE or AESI, an unscheduled visit will be organized at the investigational clinical site. Appointment for the visit 5 (day 42) will be confirmed with the participant.

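### The last sentence of 9.1.11 bars further study vaccination on suspicion of COVID-19 alone, against the confirmed-infection rule of 4.8 and the deferral in 7.2.6, and no sentence lifts the bar after a negative test

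*Protocol*

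**What the plan says.** Four places in the protocol bear on whether injection 2 is given when COVID-19 is in question.

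- **9.1.11, last sentence:** "If a subject is suspected/diagnosed with an actual COVID-19 infection he/she should not receive any subsequent study vaccination". Follow-up visits continue. Just before this, the section says: "In case, the investigator cannot rule out a COVID-19 wild type infection, SARS CoV 2 PCR and serology will be performed". It gives no consequence of a negative result.
- **4.8, individual halting rules:** the infection criterion is "Participants with a confirmed SARS CoV-2 infection given by a positive RT-PCR or a positive serology". The same list has a criterion that lets the investigator stop vaccination for a medical condition judged to pose a risk or to confound the results.
- **7.2.13, unscheduled visits:** the Belgian procedure withdraws a participant from dosing if the test is positive. After a negative PCR on site it prescribes an examination and vital signs, and it does not mention vaccination. The French procedure does not mention dosing at all.
- **7.2.6, Visit 4:** for clinically significant acute disease at the visit, or fever then or 24 hours before, "the participant may be vaccinated at a later date, at the discretion of the Investigator". The alternative is withdrawal if a halting rule of 4.8 has been met.

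Section 9.1.11 describes suspicion when it sets out who is invited for assessment and swabbing: "in case of suspected SARS-CoV-2 infection given by the presence of any symptoms listed below". A list of symptoms follows. The opening sentence of 9.1.11 is narrower. It asks for the cause to be clarified when fever, respiratory tract disease or "unexplained, severe symptoms triggering the nasal swab are reported as AE".

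**The concern.** Two sections govern the same act, a further study injection with follow-up continuing, and they set different thresholds. By joining suspected and diagnosed with a slash, 9.1.11 makes suspicion sufficient. The infection rule in 4.8 makes confirmation necessary. The 9.1.11 bar has no stated end.

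The swab-trigger symptoms include every systemic reaction that the diary solicits after injection. If the bar is applied on that description and never lifted, the participants who lose injection 2 include some who merely reacted to injection 1. The per-protocol set requires two injections (12.1) and is the set for the between-group GMT comparison (12.4). Such a loss would be related to treatment to the extent that vaccine causes more of these symptoms than placebo. It would also reduce the safety data collected after injection 2.

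**Working it through.** The plan states no figure to reproduce. The check is a comparison of the rules, followed by a few counts.

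**The rules side by side**

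| Section | Trigger | Consequence for injection 2 | Stated end of the restriction |
|---|---|---|---|
| 9.1.11, last sentence | Suspected or diagnosed | Not given | None |
| 4.8, infection criterion | Positive RT-PCR or serology | Not given | Not needed (confirmed) |
| 4.8, medical-condition criterion | Investigator's opinion | Not given | Judgment |
| 7.2.13, Belgium | Positive test | Not given | Not needed (confirmed) |
| 7.2.13, France | – | Not addressed | – |
| 7.2.6 | Fever or acute disease around Visit 4 | May be given later | Investigator's discretion, subject to 4.8 |

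**Three cases**

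1. *Positive PCR.* 9.1.11, 4.8 and the Belgian procedure agree: no further injection.
2. *Fever at Visit 4, no test result yet.* 7.2.6 allows a later injection. Fever is the first item on the 9.1.11 symptom list, so the last sentence of 9.1.11, read literally, allows none.
3. *Grade 1 or 2 symptoms after injection 1, resolved before Visit 4, PCR negative.* The infection criterion of 4.8 is not met, and the 7.2.6 deferral does not apply because the participant is now well. The literal 9.1.11 bar still stands, because nothing removes it.

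**Overlap with solicited reactions**

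- The 9.1.11 list has 20 items.
- The diary (8.2) solicits 7 systemic reactions: myalgia, rash, nausea, vomiting, fever, headache and fatigue.
- Nausea and vomiting share one list item, so 6 of the 20 items cover 7 of 7 reactions.
- Under the narrower opening sentence of 9.1.11, fever is the only one of the 7 named without a severity condition. Below grade 3 the overlap is then 1 of 7.
- At grade 3 and above 9.1.11 adds little, because 4.8 already stops "Participants who experienced a severe (grade 3 or higher) non-serious adverse event considered as at least possibly related to the vaccine".

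**Second injections under the rule (Table 1)**

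- Vaccine: cohort A 3 + 21 = 24, cohort B 3 + 21 = 24, total 48.
- Placebo: cohort C vaccinees 24, placebo recipients 3 × 6 = 18, total 42.
- All: 48 + 42 = 90.

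**Time available to resolve suspicion**

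- The first diary ends on day 14 ± 1, that is day 13 to 15.
- Visit 4 is on day 28 ± 3, that is day 25 to 31.
- The gap runs from 25 − 15 = 10 days to 31 − 13 = 18 days. A test for a diary-period symptom can normally be settled before injection 2.

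**The case against.** The strongest reply is that the harmful reading joins two sentences with different jobs. The symptom list decides who is swabbed. The vaccination sentence comes later, after work-up of the cause, exposure history, and PCR and serology where infection cannot be excluded. It also speaks of an actual infection. In that order, suspected most naturally means the investigator's conclusion after testing. This stands as the likely intent. It is nowhere written, though, and the bar covers any subsequent injection without an end point.

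Second, Visit 4 opens with a check of the individual halting rules, and 7.2.6 sends the stop decision to 4.8. A site following the visit procedure would apply 4.8, not a sentence in the pharmacovigilance chapter. This also stands, and it makes literal use of 9.1.11 less likely. The two texts still disagree.

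Third, a reader might infer that 4.8 never stops dosing without a positive test. That goes too far. Its medical-condition criterion can reach an unconfirmed case. The difference is between an investigator's judgment and a flat instruction.

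Fourth, caution is defensible in a first-in-human trial whose benefit/risk section discusses a theoretical risk of disease enhancement. That justifies withholding a dose while infection is in doubt. It does not require withholding it after infection has been excluded.

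**Conclusion.** The inconsistency is real and minor. The last sentence of 9.1.11 sets a lower threshold for stopping vaccination than the infection rule of 4.8 and the Belgian procedure. It also collides with the deferral in 7.2.6, and no sentence releases a test-negative participant.

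The size depends on how the sentence is applied. If testing resolves suspicion, the loss of second injections is near zero. If the sentence is followed literally, test-negative participants with grade 1 or 2 reactions to injection 1 could lose injection 2 and with it their place in the per-protocol set. The protocol gives no symptom rate, so no loss is estimated.

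A reader might infer from the 7-of-7 overlap that the per-protocol GMT comparison will be biased by reactogenicity. The documents do not support that. The overlap counts symptom names, not lost doses, and it needs both the broadest meaning of suspicion and a bar that outlasts a negative test. Section 8.2 reports diary symptoms as AEs only if they are moderate or severe, or mild and treated, which narrows the route further. The modified ITT safety and immunogenicity analyses keep these participants in any case.

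**What to change.** Reword the last sentence of 9.1.11 along these lines: confirmed infection, as defined in 4.8, permanently stops study vaccination; in a suspected case the injection is deferred until PCR, and serology where done, is negative and symptoms have resolved; this applies at both sites; the investigator's discretion under 4.8 is unchanged; all follow-up visits continue.

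The cost is wording in one sentence. The tests are those the protocol already orders. A deferred injection may fall outside the ± 3 day window, but 7.2.6 already accepts a later date for acute disease or fever.

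As an editorial correction in the same edit, 9.1.11 sends participants "to contact his/her GP (see section 7.2.14", a section that does not exist. The pointer should be to 7.2.13.
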